4.0 Study Intervention(s)/Investigational Agent(s)

4.1 Description:

Participants will be randomized to either the tailored QuitGuide app or the standard version of the QuitGuide app for 5 weeks. Specifically, participants will be asked to use the assigned app for one week pre-quit and 4 weeks.

Tailored QuitGuide app

This is an app not available to the public. It was developed/tailored based on an app titled QuitGuide that is available to the public and can be downloaded. Screen shots of the publicly available version, referred to as the Standard QuitGuide app, are provided as an attachment. We have also included a document describing the changes and updates that were made to the Standard QuitGuide app to develop the Tailored QuitGuide app.

Standard QuitGuide app

This is an app titled QuitGuide that is available to the public and can be downloaded and screen shots are provided as an attachment. We will not provide all photos but several options are included in the IRB submission.

4.2 Drug/Device Handling:

This study does not use a drug. The study will not be providing any device to participants. They will be expected to use their own cell phone for accessing the QuitGuide app.

4.3 Biosafety:

No biosafety concerns or reviews required.

4.4 Stem Cells:

This study does not use stem cells.

4.5 Fetal Tissue:

This study does not use fetal tissue.

5.0 Procedures Involved

5.1 Study Design:

This is a two-arm randomized clinical trial of the tailored vs standard QuitGuide app conducted.

5.2 Study Procedures:

To test feasibility, acceptability, and preliminary efficacy of the tailored QuitGuide versus standard QuitGuide for smoking cessation among AI peoples.

1. **Telephone Screener:** We will recruit AI smokers interested in quitting. Individuals will be screened over the phone for eligibility.

MEDICAL PROTOCOL (HRP-590)

PROTOCOL TITLE: QuitGuide for American Indians: Aims 2 & 3

VERSION DATE: 11-16-2022

2. **Phone-Based Baseline Interview:** If eligible, then consent will be completed. Then, participants will complete a REDCap survey (titled Baseline Survey—see below for measures). Participants will be randomized to either the *Tailored QuitGuide app* or the *Standard QuitGuide app*. Participants will be provided instruction on how to download the app to their smartphone. Upon download, all participants will be asked to provide a unique participant app ID in the app.

Randomization: Participants will be randomized with equal probability to either a tailored version of the NCI QuitGuide or a standard version of the NCI QuitGuide. Randomization will be stratified by rural/urban clinic, male/female gender, and <50 years of age/50+ years of age. Randomization will be completed using permuted block randomization with random block sizes of 2 and 4. We anticipate no or minimal block effects in our data, and therefore, we will not account for block effects in our data analysis. The randomization schedules will be created in advance.

3. **App interaction:** Upon opening the app for the first time, participants will be asked to set a quit date. All participants will set their quit date for one week later to standardize pre- and post- quit times. If smoking relapse occurs, participants will be provided the option to reset the quit date as this flexibility is permitted in the QuitGuide. Each participant will be asked to use the app for 5 weeks. Participants will have the option to contact the research coordinator at any time to report issues. At week 4, participants will be mailed a letter reminding them of the exit survey and will provide routine saliva sample collection kit with instructions to provide the sample on the same day of their exit survey, and materials (e.g., pre-paid envelope) to return the sample to the University of Minnesota for analysis.
4. **Exit Survey:** At the end of the day on the last day of the 5 weeks of app use (i.e., 5 weeks + 1 day), an automated survey link from REDCap will be sent to participants email to assess self-report outcome measures. Participants will also be called and texted to remind them to complete the survey.
5. **Optional end of study interview:** Those randomized to the tailored QuitGuide may be asked to participate in a follow-up interview to get their feedback on using the app. We expect asking up to 10 people to complete this interview.

All measures are displayed in the table:

Baseline survey collected via REDCap: Demographics, America Indian Identity Measures, Internet and smartphone use, Traditional Tobacco Use, Commercial Tobacco History, Nicotine Dependence Scale, Contemplation Ladder, Environmental Smoke Exposures, Health Literacy, Alcohol consumption, Financial Strain, Perceived Stress Scale, Brief Resilience Scale, Everyday Discrimination Scale
--

Data collected through using app and transferred from SmokeFree.gov:

All app user data. Any and all interactions with the app including days and frequency of use each day and which app components are accessed.
--

MEDICAL PROTOCOL (HRP-590)

PROTOCOL TITLE: QuitGuide for American Indians: Aims 2 & 3

VERSION DATE: 11-16-2022

Exit survey collected via REDCap: Contemplation Ladder TimeLine follow-back calendar to assess self-report CPD, use of any pharmacotherapy, 24-hour quit attempts, use of other cessation resources, Minnesota Nicotine Withdrawal Scale, Usability of App Design by System Usability Scale (SUS) Acceptability measures; plus open-ended responses on app
Audio recordings from the interviews among a subset of the participants
Saliva Sample

5.3 Study Duration:

- Individual participant duration is 5 weeks.
- The duration to enroll all study participants is 1.5 years.
- The duration for all data collection and analysis is 2.5 years.

5.4 Use of radiation:

The study does not use any radiation.

5.5 Use of Center for Magnetic Resonance Research:

The study does not use any CMMR resources.

6.0 Data and Specimen Banking

Not applicable

6.1 Storage and Access: Not applicable

6.2 Data: Not applicable

6.3 Release/Sharing: Not applicable

7.0 Sharing of Results with Participants

No study results will be shared with participants. Individual results on any collected specimens will not be shared.

8.0 Study Population

8.1 Inclusion Criteria:

- American Indian person based on self-report
- Age \geq 18 years
- Interested in quitting smoking
- Smoke \geq 3 commercial tobacco cigarette per day (CPD) in the past 30 days
 - Use of other commercial tobacco products (e.g., e-cigarettes) is permitted if they report cigarettes being their primary product
- Smartphone ownership with the ability to download applications and sufficient data to complete research procedures

8.2 Exclusion Criteria:

- New or change in pharmacotherapy for smoking cessation (includes: nicotine gum, patch, lozenge, inhaler OR medications Chantix/Wellbutrin/Zyban/Bupropion) in past month

MEDICAL PROTOCOL (HRP-590)

PROTOCOL TITLE: QuitGuide for American Indians: Aims 2 & 3

VERSION DATE: 11-16-2022

- Does not speak or read English

8.3 Screening:

Individuals are screened for eligibility by undergoing a phone screening interview with a research coordinator. The screening consists of questions about eligibility criteria. Participants who are eligible can then complete informed consent and enroll into the study—see informed consent section.

9.0 Vulnerable Populations

9.1 Vulnerable Populations:

Population / Group	Identify whether any of the following populations will be focus of the research (targeted), included, but not necessarily the focus or excluded from participation in the study.
Children	Excluded
Pregnant women/fetuses/neonates	included but not the focus
Prisoners	Excluded
Adults lacking capacity to consent and/or adults with diminished capacity to consent, including, but not limited to, those with acute medical conditions, psychiatric disorders, neurologic disorders, developmental disorders, and behavioral disorders	Excluded
Non-English speakers	Excluded
Those unable to read (illiterate)	Excluded
Employees of the researcher	included but not the focus
Students of the researcher	included but not the focus
Undervalued or disenfranchised social group	included but not the focus
Active members of the military (service members), DoD personnel (including civilian employees)	included but not the focus

MEDICAL PROTOCOL (HRP-590)

PROTOCOL TITLE: QuitGuide for American Indians: Aims 2 & 3

VERSION DATE: 11-16-2022

Individual or group that is approached for participation in research during a stressful situation such as emergency room setting, childbirth (labor), etc.	Excluded
Individual or group that is disadvantaged in the distribution of social goods and services such as income, housing, or healthcare.	included but not the focus
Individual or group with a serious health condition for which there are no satisfactory standard treatments.	included but not the focus
Individual or group with a fear of negative consequences for not participating in the research (e.g. institutionalization, deportation, disclosure of stigmatizing behavior).	included but not the focus
Any other circumstance/dynamic that could increase vulnerability to coercion or exploitation that might influence consent to research or decision to continue in research.	included but not the focus

9.2 Additional Safeguards, if any, to ensure inclusion is appropriate:

Individuals representing these vulnerable groups are not targeted for inclusion but may be included if the eligibility criteria is met. While this study is targeting American Indians, a historically disadvantaged population, members of this group should not be assumed to automatically have additional vulnerabilities.

9.3 If research includes potential for direct benefit to participants, provide rationale for any exclusions indicated in the table above:

There is potential for direct benefit of using a smoking cessation app. All exclusions listed above are related primarily to the smoking cessation app's requirements.

10.0 Local Number of Participants**10.1 Local Number of Participants to be Consented:**

Up to 116 participants will be consented at the UMN/AICAF sites—all of these will be considered UMN accrual.

MEDICAL PROTOCOL (HRP-590)

PROTOCOL TITLE: QuitGuide for American Indians: Aims 2 & 3

VERSION DATE: 11-16-2022

11.0 Local Recruitment Methods

11.1 Recruitment Process:

Recruitment will occur through social media and community events and news outlets. We also have recruited participants in one prior study (IRB: STUDY00012471: QuitGuide for American Indians: Aim 1 In STUDY00012471, we included a telephone screener form that specifically asks participants "Would you be interested in being contacted by us in the future if other research opportunities become available?". Those participants who responded "Yes" will be re-contacted by IRB approved study personnel on IRB: STUDY00012471 and reminded that they are being re-contacted due to their interest in future studies that was reported when they participated in IRB: STUDY00012471.

11.2 Identification of Potential Participants:

All participants will self-identify based on posted flyers and other recruitment materials OR recruited from IRB: STUDY00012471.

11.3 Recruitment Materials:

Pre-approved scripts and images will be used to develop flyers and postings.

11.4 Payment:

A ClinCard (Greenphire through UMN) gift card will be provided as a physical card mailed to the participant. Payment will be made as participant completes the following tasks:

Total possible compensation for all participants is \$125. Those asked to participate in a follow-up survey can receive an additional \$25.

1. Telephone Screener: No payment
2. Virtual Baseline Interview: \$25 payment
3. App interaction: No payment
4. Exit survey: \$25 if completed within 48 hours or else \$10 if completed not within 48 hours
5. Returned saliva sample: \$25 payment
6. Bonus for completing all study procedures: \$50
7. Follow-up interview among a subset of participants, invite only: \$25 additional.

12.0 Withdrawal of Participants

12.1 Withdrawal Circumstances:

Participants can choose to withdraw themselves at any time for any reason. Participants may be withdrawn by the PI if they no longer meet eligibility criteria.

12.2 Withdrawal Procedures:

If a participant is withdrawn, they will be informed and data collection will stop. All data or specimens collected up to that point will continue to be used. Compensation to that point will be provided.

MEDICAL PROTOCOL (HRP-590)

PROTOCOL TITLE: QuitGuide for American Indians: Aims 2 & 3

VERSION DATE: 11-16-2022

12.3 Termination Procedures:

If a participant is no longer eligible, they will be informed and data collection will stop. All data or specimens collected up to that point will continue to be used.

13.0 Risks to Participants

13.1 Foreseeable Risks:

The potential risks of this study are minimal and include the risks associated with the loss of confidentiality, boredom of participating, and adverse psychological events from smoking reduction/cessation due to nicotine withdrawal.

Nicotine withdrawal symptoms include sadness, difficulty sleeping, irritability, restlessness, anxiousness and are usually mild and fade with time. These symptoms present among smokers who quit in the real-world—not just exclusive to our study. The QuitGuide app has existing links to a 24-hour crisis center and information for participants to get help shall they need it as well as information on treatments (e.g., nicotine replacement therapy) to help reduce nicotine withdrawal. These resources will be maintained in the tailored version of the app. Nicotine withdrawal symptoms will be captured at the exit survey as part of an exploratory outcome via the Minnesota Nicotine Withdrawal Scale but will not be considered adverse events for this study.

Measures collected will be noninvasive and should present no psychological or medical risk to the participant. Participants will be told that they may refuse to answer any questions during baseline and follow-up surveys and they may decide to quit their participation at any time.

13.2 Reproduction Risks:

No risks to reproduction are expected with this study.

13.3 Risks to Others:

No risks to others are expected with this study.

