The objective of our primary analysis is to test the treatment effect on frequency of app initiated by the participant. Frequency of app initiated will be summarized by treatment group (tailored app vs standard app) using descriptive statistics, and analyzed using a Poisson regression model with covariates for treatment group and the three stratification factors (rural/urban clinic, male/female gender and <50 years of age/50+ years of age). Assumptions about mean and variance will be evaluated and if over-dispersion is present, negative binomial regression will be used. If data are zero-inflated, zero-inflated Poisson or negative binomial models may be considered.. This analysis will be performed using data for all participants who were randomized, while assuming non-use of app for those who did not complete the week 5 survey from the last day they launched the app.

Secondary Analysis

A secondary analysis of the primary endpoint will be performed that also adjusts for any other covariates that differ across treatment groups at baseline with a p-value less than 0.20 (covariates listed above). We acknowledge the limitations of this due to a small sample size and will take this into account when determining what additional covariates to adjust for. Additionally, a sensitivity analysis will be performed for all subjects who completed the week 5 survey.

Secondary and Exploratory Endpoint Analysis

Secondary and exploratory endpoints will be analyzed using the same approach as the primary endpoint. These endpoints will be analyzed using an appropriate regression framework (i.e. linear, logistic, Poisson etc.), adjusting only for baseline measurements of the endpoint, if available, and the three stratification factors (rural/urban clinic, male/female gender and <50 years of age/50+ years of age). Secondary analyses will consist of an adjusted analysis, as

MEDICAL PROTOCOL (HRP-590)

PROTOCOL TITLE: QuitGuide for American Indians: Aims 2 & 3

VERSION DATE: 11-16-2022

described above. All analyses will utilize residual plots and other diagnostic statistics to evaluate all modeling assumptions.

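### The Minnesota Nicotine Withdrawal Scale is given only at exit; adding it to the baseline survey would cheaply allow within-person change and a more precise comparison of arms

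*Combined protocol and SAP*

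**What the plan says.** Section 13.1 lists psychological effects of nicotine withdrawal, such as sadness, poor sleep and irritability, among the foreseeable risks. It says they "are usually mild and fade with time" and are not counted as adverse events. On measurement it says: "Nicotine withdrawal symptoms will be captured at the exit survey as part of an exploratory outcome via the Minnesota Nicotine Withdrawal Scale".

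The table of measures in section 5.2 agrees. The exit survey includes the scale. The baseline survey does not; its list ends with "Nicotine Dependence Scale, Contemplation Ladder, Environmental Smoke Exposures, Health Literacy, Alcohol consumption, Financial Strain, Perceived Stress Scale, Brief Resilience Scale, Everyday Discrimination Scale". No survey is scheduled between the two.

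On timing, section 5.2 says: "All participants will set their quit date for one week later to standardize pre- and post- quit times". The exit survey link goes out at five weeks plus one day. A participant who relapses may reset the quit date.

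For secondary and exploratory endpoints, section 15.1 plans regression on treatment group and the stratification factors, "adjusting only for baseline measurements of the endpoint, if available". Section 3.2 does not list the withdrawal scale among the exploratory endpoints, although section 13.1 calls it part of one.

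**The concern.** The scale is the only scheduled symptom measure after the quit date, and it is attached to a risk that the protocol itself names. Taken once, with no starting value, it gives a level and no change. A participant who reports sadness or poor sleep at exit may have had the same symptoms before enrolment, and the data cannot tell. The adjustment that section 15.1 offers for endpoints with a baseline value is lost for this one, although the baseline survey already carries stress, resilience and discrimination scales and the Contemplation Ladder is collected at both time points.

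At stake is how informative one exploratory measure will be. A reader of the results could also take a low exit score as a description of the first weeks after quitting, when nothing was scheduled to measure them.

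**Working it through.** **The plan's own figure.** The only computed figure in the plan is the sample size in section 15.2, for app use: rates of 35 and 35 + 3.15 = 38.15, two-sided alpha 0.05, 80% power.

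n per arm = (1.960 + 0.842)² × (35 + 38.15) / 3.15² = 57.9, so 58 per arm and 116 in total. It reproduces, and this point does not alter it.

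**Timing (section 5.2).**
- Quit date: day 7 after first opening the app.
- Exit survey link: 5 × 7 + 1 = day 36.
- Interval: 36 − 7 = 29 days, or 4.1 weeks.

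This counts both from the same start and uses the quit date first set. A reset after relapse shortens the time since the latest quit date; late completion of the survey lengthens the interval.

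**Number of measurements per participant.** Before the quit date: 0. At exit: 1. A change score needs two, so none can be formed.

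**Precision of the comparison of arms at exit.** The plan gives no SD for the scale, so differences are in SD units. With m participants per arm:

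- without a baseline: d = (1.960 + 0.842) × √(2/m)
- with a baseline covariate correlated r with the exit score: d × √(1 − r²)

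For m = 58 and no baseline, d = 2.802 × √(2/58) = 0.520. At r = 0.5, 0.520 × √0.75 = 0.451.

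The correlations are assumed; the documents give none. The loss rates are also assumed. Section 2.3 reports about 40% loss in two earlier trials delivered face to face, which may not apply to this remote trial.

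| Completers per arm | No baseline | r = 0.3 | r = 0.5 | r = 0.7 |
|---|---|---|---|---|
| 58 (no loss) | 0.520 | 0.496 | 0.451 | 0.372 |
| 46.4 (20% loss) | 0.582 | 0.555 | 0.504 | 0.415 |
| 34.8 (40% loss) | 0.672 | 0.641 | 0.582 | 0.480 |

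Residual variance falls by r²: 9%, 25% and 49%. The calculation uses the normal approximation and takes the SD as that remaining after the stratification factors.

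**The case against.** The strongest reply is that the plan gives this scale no job that it fails to do. It is exploratory, the study is classed as minimal risk, and no objective or decision rests on it. That stands, and it limits the point to an improvement.

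Several stronger readings are tempting, and the documents do not support them:

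- **That the comparison of arms is biased.** It is not. Arms are compared as randomised, and chance imbalance is already covered by the test's error rate. The missing baseline costs precision. The secondary adjusted analysis in section 15.1 may recover some of it through covariates such as nicotine dependence and cigarettes per day, if they differ between arms at p < 0.20.
- **That a baseline would show whether quitting caused symptoms.** Quitting is not randomised. A baseline gives before-and-after change, which is not enough to attribute the change to quitting.
- **That symptoms will have gone by the exit survey.** Section 13.1 says they fade but gives no time course, and the scale's recall window is not stated. Because quit dates can be reset, some participants may be early in a new attempt at exit.
- **That most scores merely reflect background mood in people who still smoke.** Section 13.1 ties the risk to cutting down as well as stopping, so scores from people still smoking may reflect withdrawal.
- **That nothing else could pick up symptoms.** Section 2.2 describes mood and craving tracking in the app, and section 5.2 says all app user data are transferred and that participants may contact the coordinator at any time. These routes are voluntary, however, and none is named as a symptom outcome in section 3.2.

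**Conclusion.** The point holds as a minor one. The withdrawal scale is taken once, about 29 days after the quit date first set, with no baseline. Within-person change cannot be computed, symptoms present before enrolment cannot be separated from later ones, and the adjustment in section 15.1 cannot be applied.

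The cost to the randomised comparison is precision. At 58 per arm the detectable difference is 0.52 SD, where a baseline would bring it to between 0.50 and 0.37 SD for assumed correlations of 0.3 to 0.7. With loss to follow-up all of these figures rise. The gain is small if the correlation is low.

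The omission of the scale from section 3.2 is a separate inconsistency with section 13.1 and needs correcting in any case. No primary or listed secondary result is affected.

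**What to change.** 1. Add the Minnesota Nicotine Withdrawal Scale to the REDCap baseline survey in section 5.2, before randomisation.
2. Analyse the exit score adjusted for the baseline score and the stratification factors, as section 15.1 already provides.
3. List the scale in section 3.2 as an exploratory endpoint.
4. State in section 15.1 that one exit score does not describe symptoms in the first weeks after quitting and does not show that quitting caused them.

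If scores are also shown by smoking status over the past 7 days, using the timeline follow-back already collected, present this descriptively only: the split is made after randomisation, and section 15.1 rules out subgroup analyses because the sample is small. Exit-survey items asking participants to recall the first week after their latest quit date are optional and subject to recall error.

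The cost is a few minutes of participant time at baseline, with no added visit or contact. Anyone enrolled before the change will have no baseline score, so it is worth making early.
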